**1 STATISTICAL CONSIDERATIONS**

A detailed and comprehensive Statistical Analysis Plan (SAP) will be prepared and signed-off before database lock. Minor changes to the statistical methods set out in this protocol

need not be reported as a protocol amendment but must be documented in the SAP and in the study report.

The statistical analysis and report will conform to the relevant ICH requirements.

## **1.1 STATISTICAL METHODS**

### **1.1.1 Summary Tables and Listings**

The standard summary statistics for continuous baseline and outcome variables are: N, mean, standard deviation, median, quartiles, minimum and maximum.

The standard summary statistics for categorical baseline and outcome variables are: count and proportion (expressed as percentage of non-missing values).

All efficacy outcomes, vital signs and laboratory assessments will be summarised by treatment group and timepoint. Baseline and demographic data will be summarised by treatment group.

The summary tables and figures will be supported by full subject listings.

### **1.1.2 Hypothesis Testing and Confidence Intervals**

All significance probabilities will be two tailed. Statistical tests will be at a 5% level of significance.

Confidence intervals will be 95% two-sided.

### **1.1.3 Randomisation and Stratification**

The center will dispense the study medication under blinded conditions according to a centrally administered, permuted block randomisation sequence (1:1 ratio for the treatment arms), managed at the study level and implemented using IWRS.

### **1.1.4 Subject Population/Sets to Be Evaluated**

It is expected that there will be an average of 3 to 4 subjects recruited per site, and hence stratification by study site could be potentially unblinding with respect to the block size given the expected difference in response rates between the two study arms. In accordance with recommendations included in ICH E9 guidelines, the randomisation will therefore be stratified by region, i.e. North America (US and Canada) and Rest of World (Europe, including Israel).

#### **All Randomised Set**

The All Randomised Set comprises all subjects which have been randomised.

#### **Safety Set**

The safety analysis (SAF) set will consist of all randomized subjects who took at least a part of one dose of study drug, and will be used for all analyses of safety.

#### **Full Analysis Set**

The full analysis set (FAS) will consist of all randomized subjects with confirmed active pouchitis at baseline, and who took at least one dose of study drug and have at least one post-

baseline assessment of efficacy. The FAS will be the primary analysis set for analyses of efficacy.

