### **Per Protocol Set**

The per protocol set (PPS) will comprise all subjects in the FAS who have not violated any major entry criteria and have not deviated significantly from the protocol during the course of the study. Any efficacy analyses from this population will be considered as supportive to those performed on the FAS. Reasons for exclusion from the PPS will be defined prospectively in the statistical analysis plan.

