### **1.3.2 Efficacy Analysis**

All efficacy analyses and summaries will be performed using the FAS. A confirmatory analysis of the primary efficacy parameter will be carried out using the PPS.

All statistical tests comparing the treatment groups will be two-tailed and at the 5% level of significance.

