#### **1.3.2.1 Co-Primary Efficacy Analysis**

The co-primary measures of efficacy will be:

- The proportion of subjects who are in endoscopic remission (Endoscopic Score  $\leq 1$ ), and
- The proportion of subjects who achieve a Stool Frequency Score  $\leq 1$ , at Week 10.

The proportion of subjects who achieve each of the co-primary measures of efficacy at Week 10 will be presented and compared between treatment groups using a Cochran-Mantel-Haenszel test accounting for region. The difference in proportions between the two groups and associated 95% confidence interval will also be presented.

Subjects with a missing endoscopic assessment at week 10, or insufficient stool frequency data, will be declared not to have achieved the respective outcomes.

Secondary analyses of the co-primary endpoints will include investigations of the effect of treatment and baseline characteristics (region, treatment, sex, age group, PDAI score) on the co-primary endpoints using logistic regression models.

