#### **1.3.2.2 Secondary and Tertiary Efficacy Analyses**

##### **Stool Frequency**

The mean daily stool frequency (frequency of bowel movement) will be evaluated from the data recorded in the subject's diary using the data from the 7 days prior to each study visit. Mean frequency and change from baseline will be summarized.

The change from baseline at each study visit will be analyzed using a mixed effects repeated measures analysis of covariance (ANCOVA) model of the change from baseline with region, treatment, Visit, treatment\*Visit interaction, sex and age group as fixed effects and baseline value as covariate.

The proportion of subjects with a Stool Frequency Score equal to 0 ('Normal number of stools per day for the subject') will be summarized and analyzed in the same way as for the co-primary endpoints.

The time to clinical remission will be summarized using Kaplan-Meier methods. Subjects without remission, (including those who withdrew from the study without remission) will be censored at the time of last assessment of the Stool Frequency Score. Kaplan-Meier curves

will be presented with estimates of the probability of remaining remission-free at Weeks 3, 6 and 10 together with their 95% confidence intervals. The time to clinical remission will be investigated using a Cox proportional hazards regression model including terms for region, treatment, sex, age group, and the baseline mean number of bowel movements per day.

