### **Urgency**

Urgency will be recorded for each bowel movement in the subject's diary as none (0), some urgency (1), great urgency (2), and subject soiled themselves, involuntarily (3). The frequency of each score in the 7 diary days prior to a study visit will be evaluated.

Changes from baseline in urgency score at week 6 will be summarized and compared between treatments.

The proportion of subjects recording urgency episodes with score 3 (fecal incontinence) after 3, 6 and 10 weeks of treatment will be analysed using logistic regression models including terms for region, treatment, sex, age group and baseline urgency.

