#### **1.3.3.4 Withdrawals**

The number (%) of subjects who withdraw from the study and their reasons for withdrawal will be tabulated by treatment group. The distribution of withdrawals and reasons will also be displayed at each visit by treatment group

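### The FAS drops dosed subjects with no post-baseline efficacy assessment, although the co-primary rule could already count them as failures

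*SAP*

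**What the plan says.** SAP 1.1.4, Full Analysis Set, sets three conditions beyond randomisation: confirmed active pouchitis at baseline, at least one dose, and at least one efficacy assessment after baseline. The definition ends "baseline assessment of efficacy. The FAS will be the primary analysis set for analyses of efficacy".

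SAP 1.3.2 gives this set full scope: "All efficacy analyses and summaries will be performed using the FAS".

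SAP 1.3.2.1 gives the missing-data rule for the co-primary endpoints: "Subjects with a missing endoscopic assessment at week 10, or insufficient stool frequency data, will be declared not to have achieved the respective outcomes".

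Two other sets matter here:
- The Per Protocol Set "will comprise all subjects in the FAS who have not violated any major entry criteria", so it lies inside the FAS.
- "The All Randomised Set comprises all subjects which have been randomised", but no analysis is assigned to that set.

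SAP 1.3.3.4 adds a descriptive table of withdrawals: "The distribution of withdrawals and reasons will also be displayed at each visit by treatment group".

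**The concern.** The failure rule needs nothing measured after baseline: a subject with no Week 10 endoscopy and no usable diary data is simply a failure. The FAS condition stops the rule from reaching the earliest leavers. A subject who leaves just before a first assessment disappears from the denominator, and one who leaves just after it stays in as a failure. The SAP gives no reason for treating the two differently.

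Having a first assessment is an event after randomisation, so treatment can influence it, for example through poor tolerability or early worsening. The same subjects leave both co-primary denominators, so unequal early loss pushes both endpoints the same way: towards alicaforsen if more are lost from that arm, and against it if more are lost from placebo. The clause gives the co-primaries nothing in return.

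**Working it through.** **Who is affected.** Diary measures are evaluated "using the data from the 7 days prior to each study visit", and the earliest post-baseline visit named for them is Week 3 (urgency is analysed "after 3, 6 and 10 weeks of treatment"). The gap therefore runs at most to about Week 3, or only a few days if any single diary entry counts as an assessment. The SAP does not say which.

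**The plan's own figures (SAP 1.2).** Inputs: 50% v 20%, two-sided 5%, 95% power, 1:1. With pooled variance under the null, n = [1.960·√(2·0.35·0.65) + 1.645·√(0.5·0.5 + 0.2·0.8)]² / 0.30² = 62.7, so 63 per arm, as stated. The continuity-corrected value is 69.2 (stated 69). Overall power is 0.95 × 0.95 = 0.9025 (stated 90%). These figures are not in dispute.

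**Assumptions for the rest.** The SAP gives neither an early-loss rate nor the region split. I assume 69 dosed per arm and treat the CMH test as one stratum without continuity correction: χ² = (x − E)²/V, with E = n₁t/N and V = n₁n₂t(N − t)/[N²(N − 1)], where x is alicaforsen successes and t total successes. Win probabilities come from exact binomial enumeration and count wins for alicaforsen only.

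**False-win rate per endpoint.** Both arms have the same true success rate r with leavers counted as failures. Dropping a alicaforsen and b placebo leavers changes the rates to 69r/(69 − a) and 69r/(69 − b).

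| r | no loss | 3 v 3 | 3 v 1 | 1 v 3 |
|---|---|---|---|---|
| 0.20 | 0.0252 | 0.0245 | 0.0308 | 0.0207 |
| 0.30 | 0.0254 | 0.0249 | 0.0325 | 0.0190 |
| 0.35 | 0.0246 | 0.0247 | 0.0314 | 0.0187 |

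**Trial level (both must win), r = 0.30, 3 v 1.** Under the independence assumed in SAP 1.2:
- Both endpoints null: 0.0254² = 0.0006 becomes 0.0325² = 0.0011.
- One null, the other truly 50% v 20%: 0.0254 × 0.9660 = 0.0246 becomes 0.0325 × 0.9755 = 0.0317.

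**Observed counts.**

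| all dosed subjects | p | after exclusion | p |
|---|---|---|---|
| 24/69 v 14/69 | 0.058 | 24/66 v 14/68 | 0.044 |
| 22/69 v 12/69 | 0.049 | 22/68 v 12/66 | 0.060 |
| 35/69 v 14/69 | 0.0002 | 35/66 v 14/68 | 0.0001 |

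First row in full:
- Before: E = 69·38/138 = 19, V = 69·69·38·100/(138²·137) = 6.934, χ² = 25/6.934 = 3.61.
- After: E = 66·38/134 = 18.716, V = 66·68·38·96/(134²·133) = 6.856, χ² = 5.284²/6.856 = 4.07.

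**Power.** Take 50% and 20% as the rates among assessed subjects, with equal early loss in both arms. Joint power is the square of the per-endpoint power.

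| early loss | kept as failures: per endpoint, joint | dropped (current FAS): per endpoint, joint |
|---|---|---|
| 0% | 0.9660, 0.933 | 0.9660, 0.933 |
| 5% | 0.9540, 0.910 (0.475 v 0.19, n = 69) | 0.9597, 0.921 (n = 66) |
| 10% | 0.9386, 0.881 (0.45 v 0.18, n = 69) | 0.9481, 0.899 (n = 62) |

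**The case against.** The strongest reply is that nothing here is a contradiction. The plan defines a set and then imputes within it, which is coherent, and an FAS of this kind is common. That is right as far as it goes. The criticism is of the choice: the plan already holds a rule that would handle these subjects, and the set definition keeps it from them.

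The number affected may be close to zero. What counts as an efficacy assessment is not defined in the SAP, and if one diary entry is enough, hardly anyone is lost. This stands, and it limits the likely harm.

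The effect needs unequal loss, its direction is unknown, and the borderline examples were chosen beside the threshold. All true. The examples show that the result can cross 0.05 in either direction, not that it probably will.

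The trial-level figures assume independent endpoints, although the same subjects leave both. Also fair. If the endpoints are positively correlated, the both-null rate exceeds the product, but it cannot exceed the single-endpoint rate. For 3 v 1 it lies between 0.11% and about 3.2%.

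Set membership is settled at a blinded review (SAP 1.1.4 and 1.4), and withdrawals are tabulated by arm and visit. Blinding prevents selective exclusion but cannot correct loss caused by treatment, and the table would reveal an imbalance without putting anyone back into the analysis.

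SAP 1 foresees a more detailed SAP, which could add a sensitivity analysis. None is planned in the present text.

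**Conclusion.** The concern holds. The primary efficacy set depends on a post-randomisation event that the co-primary endpoints do not need, and no planned efficacy analysis includes the excluded subjects. The likely effect is small. On an assumed 3 v 1 loss with equal true success of 20% to 35%, the false-win rate per endpoint goes from about 2.5% to 3.1–3.2%; on 1 v 3 it falls to 1.9–2.1%. Equal loss leaves it at about 2.5%, and a result near the planned effect is unaffected. Only a borderline result would change. The loss counts are assumptions, and confidence in the practical size is moderate. The plan should be changed because the remedy is cheap, not because serious bias is expected.

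**What to change.** For the co-primary analyses, remove from the set definition only the requirement for a post-baseline efficacy assessment. Keep the active-pouchitis and dosing conditions, and apply the failure rule of SAP 1.3.2.1 to everyone in that set. Keep the present FAS for a sensitivity analysis of the co-primaries and for the repeated-measures models, which need post-baseline data. State which set serves the other responder analyses; the Stool Frequency Score of 0 is to be analysed like the co-primaries and should follow them. Make the change before unblinding, since the two sets can give different p-values.

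The cost is wording; no new data are needed. Response rates will be slightly lower. Joint power falls from 0.921 to 0.910 at 5% early loss per arm and from 0.899 to 0.881 at 10%, so by 1 to 2 points. At 10% loss the current FAS is already marginally below the stated 90%, so the change widens that shortfall but does not create it.

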### **Per Protocol Set**

The per protocol set (PPS) will comprise all subjects in the FAS who have not violated any major entry criteria and have not deviated significantly from the protocol during the course of the study. Any efficacy analyses from this population will be considered as supportive to those performed on the FAS. Reasons for exclusion from the PPS will be defined prospectively in the statistical analysis plan.

### **Pharmacokinetically Evaluable Analysis Set**

The Pharmacokinetically Evaluable Analysis Set (PKAS) comprises all subjects receiving active treatment with sufficient blood samples taken to establish a pharmacokinetic profile and for whom the time of last dose prior to sampling is known.

The final determination of the membership of analysis sets will be made at the blinded data review meeting.

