#### **1.4 BLINDED DATA REVIEW MEETING**

The Sponsor will convene a Blinded Data Review Meeting after the data has been cleaned but before the study is unblinded. The review will be performed within the framework of the requirements of the ICH Guideline E9.

The terms of reference for the Data Review Meeting will include, but will not be limited to:

- the determination of whether protocol violations are 'major' or 'minor', or not a protocol violation at all;
- the allocation of subjects to analysis sets;
- a review of missing data and of outliers;
- a review of the distribution of the efficacy variables, considering any implications for the proposed method of statistical analysis;
- an assessment of the overall endoscopic remission rate;
- a review of whether additional covariates need to be included in the analyses;
- the finalisation of the SAP.

If the overall endoscopic remission rate indicates that the assumptions of the sample size calculation were not realized during the study then the Sponsor, taking the advice of the Data Review Meeting, may make one or more of the following changes to the primary analysis:

- changing the definition of the analysis set used;
- changing the definition of the primary endpoint;
- any other change deemed by the Sponsor as necessary to preserve the integrity of the study.

All persons taking part in the Data Review Meeting and all persons taking part in any deliberations concerning the format of the primary analysis must remain blinded to treatment allocation until any changes to the protocol specified analyses are documented and signed-off.

Formal records shall be kept of when the statistical analysis plan was finalized as well as when the blind was subsequently broken.

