#### **1.4.1 PK Parameters**

Plasma PK parameters for alicaforsen will be evaluated as follows. All consenting subjects will provide single time-point plasma samples at Day 1, Week 3 and Week 6.

In addition, full plasma concentration-time curves will be generated from a subset of randomised subjects (24 subjects, approximately 12 on active treatment and 12 on placebo) at Day 1 and Week 6. Samples from subjects in the placebo group will NOT be analyzed.

In this subset of subjects, the following PK parameters, as a minimum, will be calculated for alicaforsen:  $C_{max}$ ,  $t_{max}$ ,  $t_{1/2}$ ,  $AUC_t$ ,  $AUC_{0-24}$ ,  $AUC_{0-\infty}$ , and  $\lambda_z$ .

The following pharmacokinetic parameters will be derived:

$C_{max}$	The peak plasma concentration.
$t_{max}$	The time of peak plasma concentration.
$t_{1/2}$	The terminal half-life calculated from the terminal slope of the log concentration-time curve.
AUC	The area under the concentration-time curve will be calculated using the trapezoid rule for the interval 0 to $t_n$ h (time $t_n$ is the time at which the last non-zero level was recorded), plus the area under the exponential curve from $t_n$ h to infinity. The linear trapezoidal method will be used up to $t_{max}$ , and the logarithmic method will be used for the plasma concentrations declining from $C_{max}$ . The area from the time of last measured concentration to infinity will be extrapolated using the following formula:

$$AUC_{t_n-\infty} = \frac{\hat{C}_n}{\lambda_z}$$

where  $\lambda_z$  is the elimination rate constant calculated from non-linear regression of the terminal portion of the plasma concentration time curve, and  $\hat{C}_n$  is the predicted value of the concentration at time  $t_n$ .

Alicaforsen concentration-time curves will be plotted for individual subjects and will be summarized at Day 1 and Week 6, with concentrations on both log and linear scales. Single time-point PK data will be tabulated and summarized for each subject at Day 1, Week 3 and Week 6. Summary statistics for these data will also be computed across subjects.

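### Does the plan's only PK analysis set shut out the single time-point samples, and can a blinded meeting fix its membership?

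*SAP*

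**What the plan says.** Section 1.1.4 defines a single PK set, the Pharmacokinetically Evaluable Analysis Set (PKAS). It "comprises all subjects receiving active treatment with sufficient blood samples taken to establish a pharmacokinetic profile", and adds a third condition, that subjects are those "for whom the time of last dose prior to sampling is known". The same section closes with "The final determination of the membership of analysis sets will be made at the blinded data review meeting". Section 1.4 places that meeting before unblinding and says that those who take part "must remain blinded to treatment allocation until any changes to the protocol specified analyses are documented and signed-off".

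Section 1.4.1 plans two kinds of PK data:

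- **Single samples.** "All consenting subjects will provide single time-point plasma samples at Day 1, Week 3 and Week 6". For reporting, "Single time-point PK data will be tabulated and summarized for each subject at Day 1, Week 3 and Week 6", and "Summary statistics for these data will also be computed across subjects".
- **Full curves.** Concentration-time curves at Day 1 and Week 6 in a subset of "24 subjects, approximately 12 on active treatment and 12 on placebo". The parameters (peak, half-life, areas and so on) are derived in this subset.

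Placebo samples are not assayed. Section 1.4.1 names no analysis set for either kind of output.

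**The concern.** One sample at each of three visits, weeks apart, does not make a concentration-time profile, and the plan describes no sparse-sampling model that could turn it into one. Taken literally, active subjects outside the curve subset therefore fail the PKAS, although their concentrations are to be summarised.

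Two readings seem open, and each looks defective. If the PKAS governs the single-sample summary, most of the samples taken for it are discarded. If it does not, the summary has no named population. The requirement of a known dose time, which appears only in the PKAS definition, then does not formally reach the data that need it most, because a lone concentration is hard to interpret without the interval since dosing.

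The second worry is practical. The PKAS requires active treatment, but its membership is to be decided by people who may not know the allocation.

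At stake would be the content of the descriptive PK tables and, if the wording were forced, some pressure on the blind.

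**Working it through.** **Inputs.** 69 subjects per arm, 138 in total (section 1.2). Curve subset of 24, about 12 of them active (section 1.4.1). The consent rate for single sampling is not given, so it is varied as an assumption.

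**The plan's own figure.** 24 subjects at 1:1 gives 24 / 2 = 12 active, as stated.

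**How many would be lost if the PKAS governed the single-sample summary.** Excluded = consenting active subjects − active subjects in the curve subset.

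| Consenting active subjects (assumed) | Excluded | Share |
|---|---|---|
| 69 (100%) | 69 − 12 = 57 | 57/69 = 82.6% |
| 52 (about 75%) | 52 − 12 = 40 | 40/52 = 76.9% |
| 35 (about 50%) | 35 − 12 = 23 | 23/35 = 65.7% |

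If about 12 is taken as 10 to 14, with all 69 consenting, the excluded number runs from 69 − 14 = 55 (79.7%) to 69 − 10 = 59 (85.5%).

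**Does the plan instruct that reading?** The relevant texts, side by side:

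- The PKAS definition speaks of a profile. Section 1.4.1 produces profiles only in the curve subset, so the set and that output match.
- The single-sample paragraph draws on all who consent and calls for statistics across subjects. With placebo samples left unassayed, this means the active subjects who have a result. Nothing there mentions the PKAS or a profile condition.
- A plan that collects single samples from everyone willing, and then summarises them, would defeat itself if the summary were confined to the curve subset.

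The exclusion therefore follows only if the analyst imports a condition that section 1.4.1 does not impose.

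**Week 3.** No curves are taken at Week 3. Even on the narrow reading, the roughly 12 active curve subjects could supply Week 3 single samples, provided they consented to them, and could qualify for the PKAS through their Day 1 and Week 6 curves. Week 3 would be thinner, not empty.

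**The blinded meeting.** The PKAS has three conditions. Sample sufficiency and known dose time depend on sampling and dosing records, which exist for both arms because both arms are sampled. They can be judged blind. Active treatment is a fact of the randomisation list and needs no judgement. It can be applied mechanically once the blind is broken, without changing any decision taken at the meeting. Section 1.4 forbids disclosing allocation there, so nothing in the plan permits the harmful route.

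**The case for a change.** The strongest case for a change is that a plan should name the population for every output before concentrations are seen. Here the only PK set fits one of two outputs, the known-dose-time rule is confined to that set, and a few sentences would cure both at no cost in data. The text also gives the blinded meeting the final say on all sets with no exception for the PKAS.

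The textual part of this stands. The set for the single-sample summary is not named, the word sufficient is not defined, and the closing sentence of section 1.1.4 is loosely worded for a set that depends on arm.

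The consequences do not stand:

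- The loss of 57 subjects requires an instruction that is absent.
- A precision argument can be made: the 95% half-width for a mean is 0.635 SD with 12 subjects and 0.240 SD with 69, a ratio of 2.64. But section 1.4.1 plans summary statistics only, and the standard list in section 1.1.1 contains no confidence interval. No planned PK comparison or decision turns on that width.
- Leaving dose time out of a set definition does not mean that it goes unrecorded or is ignored. A competent PK analyst will report concentrations against the recorded time since dose and flag those without one.
- Section 1 foresees a detailed SAP before database lock, and section 1.4 lists its finalisation among the meeting's tasks. Naming the sets for descriptive tables belongs naturally to that step.

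**Conclusion.** No change to the plan follows. The mismatch is real as wording, but it is a gap that analysts fill sensibly: summarise every active subject with an analysed single sample, use the PKAS for the curves and derived parameters, take dose times from the records, and apply the arm after unblinding. Followed in that way, the descriptive PK results are sound.

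The figure of up to 57 of 69 (82.6%), or 23 of 35 to 57 of 69 across the assumed consent rates, measures what a reading the plan does not instruct would cost. It is not an expected loss. The effect on the co-primary analyses, safety analyses, sample size and type I error is nil on any reading. The conclusion assumes that dosing and sampling times are recorded for all sampled subjects. The PKAS condition on dose time suggests this, but the SAP does not state it outright.
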